4.6.2. Benefit Assessment

No medical benefit can be expected by participating in this study.

4.6.3. Overall Benefit:Risk Conclusion

GSK3039294 is an oral prodrug of CPHPC, as such it is expected to release CPHPC after oral administration. Previous clinical experience with CPHPC shows it has a good safety and tolerability profile therefore we do not anticipate safety issues linked to the release of the active moiety.

At this time, although the cardiac arrhythmias reported in Part A are unlikely to be attributable to single dose administration of GSK3039294 at either 600mg or 1200mg, as a precaution, and to further assess and confirm this conclusion, the cardiac safety monitoring of healthy volunteer subjects during repeat dose administration of GSK3039294 for 7 consecutive days in Cohort 3 Part B has been enhanced (see [Section 7.3.7.](#)), and also in systemic amyloidosis patients in Cohort 5 Part C who are known to have cardiac amyloid involvement (see [Section 7.3.8.](#)).

Biotransformation from prodrug into active will release 2 molecules of formaldehyde. There is precedent of licensed prodrugs releasing formaldehyde with no associated toxicity on a background that formaldehyde is physiologically metabolised very rapidly within the systemic circulation ([EFSA Journal, 2014; 12\(2\):3550.](#)).

Preclinical signs of potential nephrotoxicity were observed at very high doses which are unlikely to be reached in the clinic, however monitoring of renal function will be performed in the study in order to detect any potential changes.

There will be no medical benefit to healthy volunteers or patients with systemic amyloidosis being treated with GSK3039294 alone. The design of the study, schedule of assessments, and oversight mean that any risks to participants are minimised including those which might potentially affect the kidney and heart, and therefore the clinical study is justified.

5. SELECTION OF STUDY POPULATION AND WITHDRAWAL CRITERIA

Specific information regarding warnings, precautions, contraindications, adverse events, and other pertinent information on the GSK investigational product or other study treatment that may impact subject eligibility is provided in the IB for GSK3039294.

Deviations from inclusion and exclusion criteria are not allowed because they can potentially jeopardise the scientific integrity of the study, regulatory acceptability or subject safety. Therefore, adherence to the criteria as specified in the protocol is essential.

5.1. Inclusion Criteria

A subject will be eligible for inclusion in this study only if all of the following criteria apply:

All Subjects**[1] AGE**

1. 18 to 70 years of age inclusive at the time of signing the informed consent.

[2] RELEVANT HABITS

1. Non-smokers and Smokers. Smokers (<5 /day) are permitted but must be willing to abstain for the duration of residential study sessions and / or dosing period (whichever is longer).

[3] WEIGHT

1. Body weight > 50kg and body mass index (BMI) \geq 18 kg/m² (inclusive) and excluding the effects of peripheral oedema.

[4] SEX

1. Male or female
2. Female subjects are eligible to participate if they are of non-childbearing potential defined as premenopausal females with a documented tubal ligation or hysterectomy or bilateral oophorectomy; or postmenopausal defined as 12 month of spontaneous amenorrhea (in questionable cases a blood sample with simultaneous follicle stimulating hormone (FSH) > 40 MIU/ml and estradiol < 40 pg/ml (147 pmol/l) is confirmatory
3. Male subjects with female partners of child bearing potential must comply with one of the following contraception requirements from the time of first dose of study medication until completion of the follow-up visit
 - a. Vasectomy with documentation of azoospermia.
 - b. Male condom plus partner use of one of the contraceptive options below:
 - Contraceptive subdermal implant that meets the effectiveness criteria of a <1% rate of failure per year, as stated in the product label
 - Intrauterine device or intrauterine system that meets the SOP effectiveness criteria including a <1% rate of failure per year, as stated in the product label [Hatcher, 2007a]
 - Oral Contraceptive, either combined or progestogen alone [Hatcher, 2007a]
Injectable progestogen [Hatcher, 2007a]
 - Contraceptive vaginal ring [Hatcher, 2007a]
 - Percutaneous contraceptive patches [Hatcher, 2007a]
 - Occlusive cap (female diaphragm or cervical/vault cap) with a vaginal

spermicide (foam, gel, cream or suppository).

These allowed methods of contraception are only effective when used consistently, correctly and in accordance with the product label. The investigator is responsible for ensuring that subjects understand how to properly use these methods of contraception

[5] INFORMED CONSENT

1. Capable of giving signed informed consent as described in Section 10.2 which includes compliance with the requirements and restrictions listed in the consent form and in this protocol

Additional Inclusion Criteria – Healthy Volunteers

[1] TYPE OF SUBJECT

1. Healthy as determined by a responsible and experienced physician, based on a medical evaluation including medical history, physical examination, laboratory tests and cardiac monitoring.
2. A subject with a clinical abnormality or laboratory parameter(s) which is/are not specifically listed in the inclusion or exclusion criteria, outside the reference range for the population being studied may be included only if the investigator in consultation with the Medical Monitor if required agree and document that the finding is unlikely to introduce additional risk factors and will not interfere with the study procedures.
3. AST, ALT, Alkaline phosphatase and bilirubin ≤ 1.5 ULN (isolated bilirubin > 1.5 ULN is acceptable if bilirubin is fractionated and direct bilirubin $< 35\%$)

Additional Inclusion Criteria – Patients

[1] TYPE OF SUBJECT AND DIAGNOSIS INCLUDING DISEASE SEVERITY

1. Subject medically diagnosed with systemic amyloidosis
2. SAP scan identifying amyloid at any anatomical site, including subset of patients with large amyloid load in the liver
3. Up to and including NYHA class 2
4. For AL amyloidosis patients, ≥ 6 months post-chemotherapy with either a free light chain (FLC) complete response (CR) or a very good partial response (VGPR)
5. eGFR > 50 mL/min
6. Alanine amino transferase (ALT) ≤ 3 x upper limit of normal (ULN) and bilirubin ≤ 1.5 x ULN (isolated bilirubin > 1.5 xULN is acceptable if bilirubin was fractionated and direct bilirubin $< 35\%$), irrespective of alkaline phosphatase

(ALP) level

7. Subject is ambulant and capable of attending the clinical unit

Further Inclusion Criteria for Patients with known cardiac amyloid involvement

8. *eGFR* ≥ 60 mL / min
9. *Echocardiogram – LV ejection fraction* $\geq 50\%$ within 3 months of screening.

5.2. Exclusion Criteria

A subject will not be eligible for inclusion in this study if any of the following criteria apply:

All Subjects

[1] CONCOMITANT MEDICATIONS

1. Use of prohibited medication (Section 6.11.2)

[2] RELEVANT HABITS

1. History of regular alcohol consumption within 6 months of the study defined as:
 - For UK sites – healthy volunteers: an average weekly intake of >21 units for males or >14 units for females. One unit is equivalent to 8 g of alcohol: a half-pint (~240 mL) of beer, 1 glass (125 mL) of wine or 1 (25 mL) measure of spirits.

[3] CONTRAINDICATIONS

1. History of sensitivity to any of the study medications, or metabolite thereof or a history of drug or other allergy that, in the opinion of the investigator or Medical Monitor, contraindicates their participation

[4] DIAGNOSTIC ASSESSMENTS AND OTHER CRITERIA

1. **Cohort 3 (Part B) subjects only:** Cardiac arrhythmia detected on the 48hr screening Holter, with the exception of physiological bradycardia, first-degree heart block, supraventricular premature complexes and / or premature ventricular complexes (PVCs) less than a single 5-beat AIVR
2. **Cohort 3 (Part B) subjects only:** High sensitivity Cardiac Troponin level at screening > ULN for the specified assay
3. Presence of hepatitis B surface antigen (HBsAg), positive hepatitis C antibody test result at screening or within 3 months prior to first dose of study treatment.

4. A positive pre-study drug/alcohol screen (unless a positive test is due to prescribed medications)
5. A positive test for HIV antibody
6. Where participation in the study would result in donation of blood or blood products in excess of 500 mL within 84 days
7. The subject has participated in a clinical trial and has received an investigational product within the following time period prior to the first dosing day in the current study: 30 days, 5 half-lives or twice the duration of the biological effect of the investigational product (whichever is longer). Prior to Part A for subjects participating in Parts A and B
8. Exposure to more than four new chemical entities within 12 months prior to the first dosing day
9. Lactating females
10. Poor or unsuitable venous access

Additional Exclusion Criteria – Healthy Volunteer

[1] CONCURRENT CONDITIONS/MEDICAL HISTORY (INCLUDES LIVER FUNCTION AND QTc INTERVAL)

1. Current or chronic history of liver disease, or known hepatic or biliary abnormalities (with the exception of Gilbert's syndrome or asymptomatic gallstones)
2. QTcF > 450 msec from a mean of triplicate readings triplicate readings taken 5 minutes apart

Additional Exclusion Criteria – Patients

[1] CONCURRENT CONDITIONS/MEDICAL HISTORY (INCLUDES LIVER FUNCTION AND QTc INTERVAL)

1. Non-amyloid heart diseases (e.g. epicardial coronary artery heart disease, or non-amyloid valvular heart disease)
2. Subject with mean QTcF of >480ms from a mean of triplicate readings
3. **Cardiac Amyloidosis Patients ONLY** – Within 3 months of Screening, *Or* at Screening: **a).** Sustained (≥ 10 beats) / symptomatic monomorphic ventricular tachycardia (VT), or rapid polymorphic VT; **b).** Complete heart block; **c).** Brady arrhythmias deemed clinically concerning in this patient population by the Investigator in consultation with the Medical Monitor
4. Plasma albumin < 30g/litre

5. A syncopal episode, within 4 weeks of screening
6. Average SBP \leq 100mmHg at Screening from triplicate readings in Part C systemic amyloidosis patients with known cardiac amyloid involvement *Or*, Average SBP \leq 90mmHg at Screening from triplicate readings in systemic amyloidosis patients *without* known cardiac amyloid involvement
7. Implantable cardiac defibrillator (ICD)
8. Insertion of permanent pacemaker in last 2 months
9. Decompensated or uncontrolled heart failure in last 2 months
10. Anaemia Hb $<$ 9g/dL
11. Uncontrolled hypertension in a known hypertensive patient, or fulfilling diagnostic criteria of essential hypertension at screening
12. Presence of any co-morbid condition (e.g. severe or unstable coronary artery disease; moderate to severe chronic obstructive pulmonary disease) which in the opinion of the investigator would increase the potential risk to the subject
13. Non-amyloidosis causes of chronic liver disease (with the exception of Gilbert's syndrome or clinically asymptomatic gallstones)
14. Diabetes Mellitus
15. Glycosuria at Screening
16. Urine pH $<$ 6.0 at screening
17. Hypoalbuminaemia ($<$ 30nmol/L)
18. Hypophosphatemia (less than 0.8mmol/L)
19. Prothombin time $>$ 1.5xULN
20. Malabsorption syndrome of any aetiology

[2] CONCOMITANT MEDICATIONS

1. Compassionate use of CPHPC or participation in a separate clinical trial involving CPHPC within 3 months of screening
2. Currently taking any of the following esterase-cleaved prodrug medications: cerebyx, aquavan, spectracef, hepsera, viread
3. Anticoagulation therapy within 4 weeks of Screening
4. Currently receiving or have received within 12 weeks of screening immunosuppressive anti-cytokine monoclonal antibodies (e.g. anti-TNF or anti-IL-1), disease modifying drugs (e.g. methotrexate, gold or cyclophosphamide), or high-dose infusional steroids (e.g. methylprednisolone), with the exception of low-dose maintenance oral corticosteroids (e.g. ≤ 30 mg prednisolone per day)

5.3. Screening/Baseline/Run-in Failures

Screen failures are defined as subjects who consent to participate in the clinical trial but are never subsequently enrolled. In order to ensure transparent reporting of screen failure subjects, meet the Consolidated Standards of Reporting Trials (CONSORT) publishing requirements, and respond to queries from Regulatory authorities, a minimal set of screen failure information is required including Demography, Screen Failure details, Eligibility Criteria, and any Serious Adverse Events.

5.4. Withdrawal/Stopping Criteria

The following actions must be taken in relation to a subject who fails to attend the clinic for a required study visit:

- The site must attempt to contact the subject and re-schedule the missed visit as soon as possible.
- The site must counsel the subject on the importance of maintaining the assigned visit schedule and ascertain whether or not the subject wishes to and/or should continue in the study.
- In cases where the subject is deemed 'lost to follow up', the investigator or designee must make every effort to regain contact with the subject (where possible, 3 telephone calls and if necessary a certified letter to the subject's last known mailing address or local equivalent methods). These contact attempts should be documented in the subject's medical record.
- Should the subject continue to be unreachable, only then will he/she be considered to have withdrawn from the study with a primary reason of "Lost to Follow-up".

Non-compliance to the study regimen or withdrawal of consent (no reason has to be given by the individual subject) will lead to the removal from the study. An individual subject may withdraw from study treatment at any time at his/her own request, or may be withdrawn at any time at her own request, or at the discretion of the investigator for safety, behavioural or administrative reasons. If a subject withdraws from the study, he/she may request destruction of any samples taken, and the investigator must document this in the site study records. The entire study will be terminated if the sponsor (GSK) stops the study at any stage.

Individual subjects may be withdrawn at the investigator's discretion at any time during the study, provided there is a valid and confirmable clinical reason. The presence of severe AEs predefined as stopping criteria below in Section 5.5, or SAE as defined in [Appendix 3](#), will lead to the withdrawal of an individual subject. Withdrawn subjects will be replaced by new subjects as per the guidance in Section 6.4

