3. OBJECTIVE(S) AND ENDPOINT(S)

Part A: Single ascending dose in healthy volunteers

Objectives	Endpoints
Primary	
Evaluate safety and tolerability of single doses of GSK3039294	Adverse events, laboratory measurements, ECG, vital signs and cardiac telemetry (where applicable)
Secondary	
Evaluate pharmacokinetics of single doses of GSK3039294 and its biotransformation into GSK2315698 (CPHPC)	PK parameters of GSK2315698 and GSK3039294

Part B: Repeat dose in healthy volunteers

Objectives	Endpoints
Primary	
Evaluate safety and tolerability of repeat doses of GSK3039294	Adverse events, laboratory measurements, ECG, vital signs and cardiac telemetry (where applicable)
Secondary	
Evaluate pharmacokinetics of repeat doses of GSK3039294 and its biotransformation into GSK2315698 (CPHPC)	PK parameters of GSK2315698 and GSK3039294
Pharmacodynamic effect of repeat doses of GSK3039294 on plasma SAP levels	Plasma SAP levels
Explore correlation of dose of GSK3039294, blood concentration of GSK2315698 and plasma SAP levels	PK parameters of GSK2315698 and GSK3039294 Plasma SAP levels
Exploratory	
Determine the effect of food on a single dose of GSK3039294	PK parameters of GSK2315698 and GSK3039294 under fasted and fed conditions.

[figure not shown]
Part C: Repeat dose in patients with systemic amyloidosis

Objectives	Endpoints
Primary	
Evaluate safety and tolerability of repeat doses of GSK3039294	Adverse events, laboratory measurements, ECG, vital signs
Secondary	
Evaluate pharmacokinetics of repeat doses of GSK3039294 and its biotransformation into GSK2315698 (CPHPC)	PK parameters of GSK2315698 and GSK3039294
Pharmacodynamic effect of multiple doses of GSK3039294 on plasma SAP levels	Plasma SAP levels and time to repletion of SAP.
Explore correlation of dose of GSK3039294, blood concentration of GSK2315698 and plasma SAP levels	PK parameters of GSK2315698 and GSK3039294 Plasma SAP levels

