4.2.3.1. Sentinel Dosing in Part C

[figure not shown]
Renal Amyloidosis Sentinel Subject: A sentinel systemic amyloidosis patient (n=1) with known renal involvement and an estimated GFR ≥ 60 ml / min, *but with no known cardiac involvement*, will be dosed repeatedly with GSK3039294 for the full 21-day period before dosing any other patients begin. Following this, dosing of other patients with renal involvement (with an eGFR > 50 mL / min) but with no cardiac involvement can be initiated, provided no concerning safety signals are detected in this sentinel patient.

Cardiac Amyloidosis Sentinel Subject: Once the sentinel renal patient has successfully completed dosing, a sentinel cardiac amyloidosis patient (n=1) with eGFR ≥ 60 mL / min & LV Ejection Fraction (EF) $\geq 50\%$ will be dosed repeatedly with GSK3039294 for the full 21-day period. Following this, dosing of any other patients with cardiac involvement (NYHA ≤ 2) can be initiated provided no concerning safety signals are detected in the sentinel cardiac patient.

Table 4 Cohort 5 Study Duration

Screening	All screening assessments to be completed within 28 days prior to the first dose including out-patient cardiac monitoring for 7 continuous days (with external portable monitoring device) only in those patients with known cardiac amyloid involvement
Treatment Period	Each subject will take part in a single study period. Subjects will be in-patient from Day -1 until Day 8 when they will be discharged after assessments have been completed. In-patient cardiac telemetry will be performed from at least Day -1 until Day 8 only in those patients with known cardiac amyloid involvement. Subjects will return to the unit as out-patients for regular assessments whilst continuing dosing to Day 21.
Safety Follow-up	Subjects will attend 7-14 days post last dose for a safety follow-up
PD Follow-up	Weekly PD assessments will be made up to 42 days after last study drug administration Additional follow-up visits may be scheduled, if warranted
Total Duration	Approximately 13 weeks

Figure 4 Illustrative Schematic of Proposed Study Design for Patient Subjects Repeat Dose (Cohort 5)

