6.7. Compliance with Study Treatment Administration

When the individual dose for a subject is prepared from a bulk supply, the preparation of the dose will be confirmed by a second member of the study site staff.

When subjects are dosed at the site, they will receive study treatment directly from the investigator or designee, under medical supervision. The date and time of each dose administered in the clinic will be recorded in the source documents. The dose of study treatment and study subject identification will be confirmed at the time of dosing by a member of the study site staff other than the person administering the study treatment. Study site personnel will examine each subject's hands and mouth to ensure that the study treatment was ingested.

When subjects self-administer study treatment(s) at home, compliance with GSK3039294 will be assessed through a dosing record, querying with the subject during the site visits and documented in the source documents and CRF. A record of the number of GSK3039294 capsules dispensed to and taken by each subject must be maintained and reconciled with study treatment and compliance records. Treatment start and stop dates, including dates for treatment delays and/or dose reductions will also be recorded in the CRF.

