7.3.1.1. Time period and Frequency for collecting AE and SAE information

- AEs and SAEs will be collected from the start of Study Treatment until the follow-up contact (see Section 7.3.1.3), at the timepoints specified in the Time and Events Table (Section 7.1).
- Medical occurrences that begin prior to the start of study treatment but after obtaining informed consent may be recorded on the Medical History/Current Medical Conditions section of the CRF.
- Any SAEs assessed as related to study participation (e.g., protocol-mandated procedures, invasive tests, or change in existing therapy) or related to a GSK product will be recorded from the time a subject consents to participate in the study up to and including any follow-up contact.
- All SAEs will be recorded and reported to GSK within 24 hours, as indicated in [Appendix 4](#).
- Investigators are not obligated to actively seek AEs or SAEs in former study subjects. However, if the investigator learns of any SAE, including a death, at any time after a subject has been discharged from the study, and he/she considers the

event reasonably related to the study treatment or study participation, the investigator must promptly notify GSK.

NOTE: The method of recording, evaluating and assessing causality of AEs and SAEs plus procedures for completing and transmitting SAE reports to GSK are provided in [Appendix 4](#)

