7.3.1.3. Follow-up of AEs and SAEs

After the initial AE/SAE report, the investigator is required to proactively follow each subject at subsequent visits/contacts. All SAEs, and non-serious AEs of special interest (as defined in Section 4.6.1) will be followed until resolution, until the condition stabilizes, until the event is otherwise explained, or until the subject is lost to follow-up (as defined in Section 5.4). Further information on follow-up procedures is given in [Appendix 4](#).

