21	Pre-dose, and 0.5; 1; 2; 3; 4; 6; 8 and 12 hrs post-dose (1 st dose; note: 12hr post dose sample to be taken before

Study Day	PD sampling timepoint(s)
	next dose administration)
Safety Follow-up	Single sample
PD Follow-up	1 sample/wk up to 6 weeks

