
 • Immediately discontinue study treatment • Report the event to GSK within 24 hours • Complete the liver event CRF, and complete an SAE data collection tool if the event also meets the criteria for an SAE² • Perform liver event follow up assessments • Monitor the subject until liver chemistries resolve, stabilise, or return to within baseline (see MONITORING below) • Do not restart/rechallenge subject with study treatment. Permanently discontinue study treatment and may continue subject in the study for any protocol specified follow up assessments 
MONITORING:
 
If ALT\geq3xULN AND bilirubin \geq 2xULN or INR >1.5:
 
 • Repeat liver chemistries (include ALT, AST, alkaline phosphatase, bilirubin) and perform liver event follow up assessments within 24 hrs • Monitor subjects twice weekly until liver chemistries resolve, stabilise or return to within baseline • A specialist or hepatology consultation is recommended 
If ALT\geq3xULN AND bilirubin < 2xULN and INR \leq1.5:
	
 • Viral hepatitis serology³ • Blood sample for pharmacokinetic (PK) analysis, obtained within 48 hours of last dose⁴ • Serum creatine phosphokinase (CPK) and lactate dehydrogenase (LDH). • Fractionate bilirubin, if total bilirubin\geq2xULN • Obtain complete blood count with differential to assess eosinophilia • Record the appearance or worsening of clinical symptoms of liver injury, or hypersensitivity, on the AE report form • Record use of concomitant medications on the concomitant medications report form including acetaminophen, herbal remedies, other over the counter medications. • Record alcohol use on the liver event alcohol intake case report form 
If ALT\geq3xULN AND bilirubin \geq 2xULN or INR >1.5:
 
 • Anti-nuclear antibody, anti-smooth muscle antibody, Type 1 anti-liver kidney microsomal antibodies, and quantitative total immunoglobulin G (IgG or gamma globulins).

Liver Chemistry Stopping Criteria – Liver Stopping Event	

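### Section 5.4 removes a non-compliant but still consenting subject from the study, not only from treatment, so the scheduled safety follow-up and, in Part C, the post-dosing plasma SAP samples are lost (minor)

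*Protocol*

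**What the plan says.** Section 5.4 puts two different events in one sentence with one consequence: "Non-compliance to the study regimen or withdrawal of consent (no reason has to be given by the individual subject) will lead to the removal". The sentence ends by naming the study, not study treatment, as what the subject is removed from. The next sentence mentions withdrawal from study treatment at the subject's own request, and withdrawal at the investigator's discretion for safety, behavioural or administrative reasons. Withdrawn subjects are to be replaced.

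Section 6.7 says how compliance is judged during home dosing: a dosing record, questions at visits and a capsule count. It gives no threshold for non-compliance. It adds: "Treatment start and stop dates, including dates for treatment delays and/or dose reductions will also be recorded in the CRF".

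In Part C, patients are discharged on Day 8 and dose as out-patients to Day 21 (Table 4). After dosing, Table 4 says: "Weekly PD assessments will be made up to 42 days after last study drug administration". Table 10 lists one SAP sample at the safety follow-up and, for the PD follow-up, "1 sample/wk up to 6 weeks". The Part C endpoints in Section 3 include "Plasma SAP levels and time to repletion of SAP".

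On safety, Section 7.3.1.1 says: "Investigators are not obligated to actively seek AEs or SAEs in former study subjects". Section 7.3.1.3 says: "All SAEs, and non-serious AEs of special interest (as defined in Section 4.6.1) will be followed until resolution", or until one of the other listed end points. Section 6.8 has its own monitoring rule for overdose.

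For patients with a liver stopping event, Appendix 2 (Section 12.2.2) takes a different line: "Permanently discontinue study treatment and may continue subject in the study for any protocol specified follow up assessments".

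**The concern.** Non-compliance is a fact about taking capsules. Withdrawal of consent is a decision to leave. A subject can do the first without the second, and such a subject has been exposed to the drug and may well attend further visits. Removing that subject from the study ends data collection that does not depend on further dosing.

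Two things are at stake. Safety is the primary objective in every part, and scheduled detection of new events after the last dose would be confined to subjects judged compliant. In Part C, SAP recovery can be observed only after dosing stops, so a patient removed before then contributes nothing to time to repletion. Section 2.2 says recovery time depends on amyloid load, and Part C plans a minimum of 12 patients, so individual recovery curves carry information.

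**Working it through.** **Does any other text keep the subject in follow-up?**

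- Section 5.4, the rule itself: mandatory wording, and the object is the study.
- Section 5.4, next sentence: discretionary withdrawal for behavioural reasons. It can be read as treatment-only, but it does not say that visits continue.
- Section 12.2.2: stop treatment and stay for follow-up, but only for patients after a liver stopping event.
- Section 4.2.2.3: Cohort 4a subjects withdrawn for adverse events are followed as per local practice. This does not cover non-compliance.
- Sections 7.3.1.3 and 6.8: known SAEs and AEs of special interest are followed, and overdose is monitored. Neither schedules visits for a removed subject.

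No current text schedules follow-up for a consenting subject removed for non-compliance.

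**What one removed Part C patient loses.** Out-patient visits are read from Section 7.1.5 as Days 12, 15, 18 and 21. The Day 8 pre-dose sample is counted, because patients are still in the unit that day and the tables ask for a sample on Days 8-20 when a visit is planned.

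SAP samples (Table 10):

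- Total: Day 1, 5; Days 2-7, 6; Day 8, 1; Days 12, 15 and 18, 3; Day 21, 9; safety follow-up, 1; weekly, 6. Sum: 5 + 6 + 1 + 3 + 9 + 1 + 6 = 31 (30 without Day 8).
- Removed after the Day 12 sample: 2 + 9 + 1 + 6 = 18 lost; 18/31 = 58% (18/30 = 60%).
- Removed after the Day 18 sample: 9 + 1 + 6 = 16 lost; 16/31 = 52% (16/30 = 53%).
- Post-dosing only: 1 + 6 = 7 of 7 lost, or 6 of 6 if the safety sample coincides with a weekly one. In that case the totals and the losses above each fall by one.

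PK samples (Section 7.4.1):

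- Total: 14 + 6 + 1 + 3 + 9 + 2 = 35 (34 without Day 8).
- Removed after Day 12: 2 + 9 + 2 = 13 lost; 13/35 = 37%.
- Removed after Day 18: 9 + 2 = 11 lost; 11/35 = 31%.

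Nine of the lost samples in each set are the Day 21 profile, which is meaningful only if dosing continued.

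**What one removed Cohort 4 subject loses** (no dose change). The visits lost are the mid-period out-patient visit with its safety assessments (if removal comes before it), the Day 21 visit and the follow-up visit. PK: 2 + 3 + 7 + 9 + 1 = 22 in total, and 9 + 1 = 10 lost. SAP: 2 + 2 + 2 + 1 = 7 in total, and 1 lost. Table 9 has no Day 21 SAP sample for Cohort 4, and repletion is not an endpoint there.

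**Effect on precision, for scale.** Section 9.2.1.2 gives an upper-limit factor of 2.57 for 6 subjects and a log-scale SD of 0.9. The formula exp(t(0.975, n-1) × SD / √n) gives 2.572, so the figure reproduces. With the same SD, the factor is 1.77 for n = 12 and 1.83 for n = 11. One unreplaced patient therefore costs little precision.

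**How often.** The protocol gives no rate. If 5%, 10% or 20% of patients were judged non-compliant (assumed values), the chance of at least one among 12, 1 - (1 - p)^12, would be 46%, 72% or 93%. This says how often the rule might act, not how large any bias would be.

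**The case against.** The strongest reply is that the rule is softer than it looks. Behavioural reasons are a natural heading for non-compliance, the sentence that names them opens with study treatment, and it leaves the decision to the investigator. The recording of delays and dose reductions in Section 6.7 suggests that minor lapses are tolerated. This stands in part. A reader might infer that any missed dose forces removal, or that the protocol knows no treatment-only withdrawal; the documents support neither. But discretion in one sentence does not cancel a mandatory consequence in the sentence before it, and neither sentence provides for continued visits.

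Second, the safety loss is partly covered. AEs are collected until the follow-up contact, with no stated exception for non-compliance. Follow-up is timed from the last dose, and extra visits may be scheduled if warranted. A site could therefore still see the subject. That is possible but not required, and a removed subject falls naturally under the statement on former study subjects. It would be wrong to infer that all safety follow-up stops: the loss is the scheduled search for new events.

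Third, repletion after irregular dosing starts from an uncertain degree of depletion, and subjects who took the planned regimen are the right group for judging 21-day maintenance. This also stands. It limits the value of the recovered samples but does not make them worthless, and the model-based analysis works from actual times.

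Finally, sample counts for one hypothetical subject are not a measure of harm. That is correct.

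**Conclusion.** The point holds as a minor design weakness. Followed as written, Section 5.4 ends scheduled follow-up for a consenting subject judged non-compliant. In Part C this removes every post-dosing SAP sample for that patient, and with them the time-to-repletion observation. The avoidable loss is those 7 (or 6) samples and the safety follow-up visit; the Day 21 profile is not avoidable once dosing has stopped.

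A reader might go further and conclude that the late safety or repletion results will be biased, or that removed subjects vanish from the analysis. The documents do not support this. No non-compliance rate is given, no hypothesis is tested, and data collected before removal stay in the Section 9.3.1 populations. Replacement of withdrawn subjects protects the numbers, though it does not bring back data from those already exposed.

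The conclusion assumes that the rule acts on subjects the investigator judges non-compliant, and that the Part C visit days are as read above.

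**What to change.** Amend Section 5.4 so that non-compliance may lead to stopping study treatment at the investigator's discretion but does not by itself remove the subject from the study. Unless consent is withdrawn, the subject then completes the safety follow-up already scheduled and, in Part C, the PD follow-up counted from the actual last dose. Table 4 already counts from the last dose; for a patient who doses to Day 21, 42 further days give the Day 63 shown in Section 7.1.5.

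The cost is a sentence or two in an amendment. No new visit or procedure type is needed, and dosing records and capsule counts are already collected. The downside is somewhat more variable late SAP and PK data that rely on self-reported dosing. How those data are summarised or modelled can be left to the Reporting and Analysis Plan.
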